6.2.3 Blinding

In order to reduce the chance for bias, research staff implementing this study will either be blinded to treatment assignment or not. Blinded staff will be involved in activities that will ensure those individuals remain blinded throughout the study. Unblinded staff will perform activities that will require knowledge of the participants study arm. The specific roles and personnel are listed in the Delegation of Authority Log.

PIs, data collectors and the study statistician will remain blind to group allocation until the database is locked. PIs and research staff will not have access to the randomization list. Blinding of all study research assistants is not possible with this study design, as they will be interacting with participants via phone calls and the nature of the discussion may disclose the type of recordings the participant is using (i.e., white noise or hypnosis intervention with induction). Approximately one to three staff members will be unblinded and perform the randomization, education and follow up phone calls. The data is self-reported by the participants and will be mailed back to the research site, where an unblinded research staff member will receive it upon completion.

A limited number of research staff will be identified on the Delegation of Authority Log as **unblinded research staff**, and will be authorized to:

- Inform of randomization assignment
- Administer the EHS
- Provide initial education regarding implementing assigned arm
- Provide telephone follow up calls
- Prepare required quarterly/annual reports to NCCIH, DSMB, and IRB
- Other tasks as delegated in the Delegation of Authority log

Participants will also be blinded to the study hypotheses to avoid bias regarding what is the experimental treatment versus control arm. After the 12-week data point, participants in the self-administered sham white noise hypnosis arm who have completed the study and returned all data will be offered the set of hypnosis audiotapes.

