Eligible participants will be randomized to either self-administered hypnosis intervention or selfadministered sham white noise hypnosis which includes listening to white noise. Randomization will be accomplished by the statistical team using stratified permuted block randomization with fixed blocks of size four. Two strata will be used: site (University of Michigan or Baylor University) and participant subgroup (post-menopausal or breast cancer). All randomization block permutations will be generated, and one permutation will be randomly assigned to each block. The randomization information will be printed on individual cards, each of which will be placed in a brown security envelope and sealed (one card per envelope). The envelopes will be chronologically numbered and assigned according to that order. It is expected that each site (Baylor University and University of MI) will each recruit approximately half of the participants, but each site will receive two sets of 116 envelopes – one set of 116 for each participant subgroup. It is not expected that there be an equal distribution of participants who are post-menopausal or breast cancer survivors; rather, the randomization strategy ensures an equal distribution of each subgroup into the self-administered hypnosis intervention or self-administered sham white noise hypnosis condition regardless of the proportion of each participant subgroup within site. For example, if Baylor University randomizes 100 participants who are post-menopausal and 16 who are breast cancer survivors, having two sets of 116 randomization envelopes ensures that (1) there are enough envelopes and (2) there are 50 postmenopausal and 8 breast cancer survivors in each condition. Therefore, one set of sealed envelopes for post-menopausal participants with group assignment and one set of sealed envelopes for breast cancer survivors with group assignment will be provided to both [name] team and [name] team. The randomization list will be kept by the statistician and person(s) who will randomize participants, educating them about their treatment assignment, and not accessible to persons who will be educating, obtaining consent from the participants, collecting data, or interacting in any other capacity which involves contact with participants, as this may possibly cause bias in the recruitment process. The unused randomization envelopes will be destroyed.

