Eligible participants will be randomized to either self-administered hypnosis or self-administered sham white noise hypnosis. Randomization and mailing of appropriate intervention materials will take place several days before the visit if the visit is to take place through phone or video conference due to COVID-19 restrictions. Participants will also have an option of having the appropriate intervention materials shared with them electronically. Education about implementing their assigned arm will take place and for those assigned to hypnosis, the hypnotizability scale will be administered. However, the hypnotizability scale will not be administered if the randomization visit takes place through phone or video conference due to COVID-19 restrictions. Randomization will be

accomplished by the development of equally distributed tables of random numbers by the statistical team.

It is expected that each site (Baylor University and University of MI) will each recruit approximately half of the participants. Accrual will be closely monitored and efforts to randomize an equal number at each site will be made (see Section 9.4). Should accrual and randomization at either site significantly exceed 50% then the accrual percentage will be reduced at the other site accordingly. The randomization list will be kept by the study statistician.

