randomly assigned to each block. Given that block size will be fixed at four, there are six permutations of randomization. One of the six permutations will be randomly to each block of participants. The randomization information will be printed on individual cards (e.g., "46BRG32: Self-Administered Hypnosis Group" or "46BRG32: Self-Administered Sham White Noise Hypnosis Group"), each of which will be placed in a brown security envelope and sealed (one card per envelope). It is expected that each site (Baylor University and University of MI) will each randomize approximately half of the participants, but each site will receive two sets of 116 envelopes – one set of 116 for each participant subgroup. It is not expected that there be an equal distribution of participants who are post-menopausal or breast cancer survivors; rather, the randomization strategy ensures an equal distribution of each subgroup into the self-administered hypnosis intervention or self-administered sham white noise hypnosis condition regardless of the proportion of each participant subgroup within site. For example, if Baylor University randomizes 100 participants who are post-menopausal and 16 who are breast cancer survivors, having two sets of 116 randomization envelopes ensures that (1) there are enough envelopes and (2) there are 50 post-menopausal and 8 breast cancer survivors in each condition. Therefore, one set of sealed envelopes for post-menopausal participants with group assignment and one set of sealed envelopes for breast cancer survivors with group assignment will be provided to both [name] team and [name] team. The case assignment spreadsheets will be kept by the statistician, and not accessible to persons who will be educating, obtaining consent from the participants, collecting data, or interacting in any other capacity which involves contact with participants, as this may possibly cause bias in the recruitment process. All participants randomized will be included in the analyses (i.e., intent-to-treat analysis).

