The baseline Hot Flash Daily Diary, saliva, and the HRV monitor will be mailed to the lab at the end of the baseline week. These materials can also be submitted electronically if the randomization/education visit takes place by telephone or video conference during the COVID-19 restrictions. If the visit takes place in person (at a time when COVID-19 restrictions are not in place), it may be brought to the lab at the time of the randomization/education visit. Staff receiving the data will be blinded to group assignment of the participant returning the data collection materials, and data will be entered upon receipt by a blinded data collector.

Before week 6, a package will be mailed to the participant with cortisol collection materials and an HRV monitor. At the end of Week 6, participants will complete the outcome measures in the Questionnaire Booklet, a second 2-day cortisol collection and wear the HRV for the designated time at some point during the two-day cortisol collection period. Once the questionnaires and physiological data collection is complete, participants will return to the lab in a pre-paid mailer:

• Six, week-long Hot Flash Daily Diaries

- The Self-Hypnosis Practice Log
- Questionnaires Booklet
- Cortisol collection materials
- HRV monitor

However, if this collection was optional or unable to be completed due to COVID-19 restrictions, saliva samples and HRV data will not be collected at this time.

During Week 11, a phone call will be made to participants to remind them of the 12 week data collection which includes a 7-day Hot Flash Daily Diary, 7-Day Self-Hypnosis Practice Log, and self-report questionnaires. This will all be in the toolkit with a pre-paid mailer. At the end of the Week 12, participants will complete the questionnaires and return the Hot Flash Daily Diary, Self-Hypnosis Practice Log, and Questionnaire booklet.

Data collectors, individuals responsible for data entry, PIs, and the study statistician will be blinded to the participants' group assignment, but the research staff who will randomize and research assistants who will call participants will be aware of the participant's group assignment. Participants will also be blinded to the study hypotheses to avoid bias regarding what is the experimental treatment versus control arm.

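### The study statistician is to stay blind until database lock, yet three sections make the statistician the keeper of the allocation records, so that blinding is not secured as written

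*Combined protocol and SAP*

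**What the plan says.** **On the statistician's blinding.** Section 6.2.3 (Blinding): "PIs, data collectors and the study statistician will remain blind to group allocation until the database is locked". Section 10.1 says the same without the time limit: "Data collectors, individuals responsible for data entry, PIs, and the study statistician will be blinded".

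**On custody of the allocation records.** Section 3: "The randomization list will be kept by the statistician and person(s) who will randomize participants". Section 4.3: "The randomization list will be kept by the study statistician". Section 9.3, under treatment assignment: "The case assignment spreadsheets will be kept by the statistician". The same part of Section 9.3 gives a sample randomisation card, "46BRG32: Self-Administered Hypnosis Group", on which a code stands beside the arm in plain words.

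**On receipt of returned data.** Section 6.2.3 describes self-reported data being mailed to the site, "where an unblinded research staff member will receive it upon completion". Section 10.1 says: "Staff receiving the data will be blinded to group assignment of the participant returning the data collection materials", and adds that a blinded data collector enters the data.

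**The concern.** A statistician cannot both keep the record of who was assigned to what and be blind to it until lock, unless some barrier separates the two roles. The protocol describes no such barrier.

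This matters where the plan leaves the analyst room to decide:

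- **Covariates.** Section 9.7 says potential confounders can be added to the longitudinal model. It gives race/ethnicity and education only as examples of an open-ended list.
- **Missing data.** The opening of Section 9.7 commits to multiple imputation. The Missing Data text in the same section makes it conditional on signs of systematic bias and words it as something that would probably be considered.

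Both reach the primary hot flash analysis. A reader of the results would want to know that they were settled without sight of the arms. If the trial reports a blinded statistician, its own protocol gives reason to doubt it.

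A secondary matter is that Sections 6.2.3 and 10.1 describe the person who receives returned data differently.

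**Working it through.** No figure is in dispute, so the check compares the sections.

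1. **Is it the same role?** Sections 4.3, 6.2.3 and 10.1 all use the term study statistician. Sections 3 and 9.3 say the statistician. The Preface describes one person who is co-investigator and statistician, and the Missing Data text refers to a single statistician for the analysis. A statistical team is mentioned in Sections 3, 4.3 and 9.3, but none of its members is described as an unblinded custodian. Two statements of blinding (6.2.3, 10.1) stand against three of custody (3, 4.3, 9.3).

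2. **Do the records show the arm?** The sample card names the arm. No A/B or similar masking is described for the list, the spreadsheets or the analysis file.

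3. **Does the list identify each participant's arm?** Not by itself. There are 2 sites × 2 subgroups × 116 envelopes = 464 prepared assignments. Section 9.3 plans for 232 participants and the Preface for 247, so the list is longer than the trial on either count. It links an envelope to an arm; a second link, from participant to envelope, is still needed. Section 3 says envelopes are numbered and used in order, so the order of randomisation within a stratum would supply that link. The case assignment spreadsheets might also contain it, but their content is not described. Access is therefore possible; knowledge of every arm is not shown.

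4. **Who is kept from the records?** Sections 3 and 9.3 bar staff who have contact with participants. Neither bars the statistician. Section 6.2.3 also denies research staff the list, while Section 3 gives it to those who randomise, so these two need aligning as well.

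5. **Would masked codes be enough?** No. The hypnotizability scale is given only to the hypnosis arm (Section 3, Table 4 and Section 6.2.2.2). If codes A and B are used and scores appear under one of them only, that code is the hypnosis arm. Comments in the practice log, which both arms complete, may also describe the recording.

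6. **Receipt of data.** The Section 6.2.3 sentence is general. The Section 10.1 sentence closes a paragraph on baseline materials. Under Section 6.2.2.3 randomisation follows the baseline measures, so blinding receivers to group at baseline alone would achieve little, and the sentence may be meant generally. On the general reading the two conflict; on the narrow one they need not.

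**The case against.** The best reply is that a wording slip is being read as a breach. The intention to blind is stated twice, a statistical team exists, and specific roles are placed in a Delegation of Authority Log that is not part of these documents. That log may assign custody to someone else. This stands to the extent that actual unblinding cannot be shown from a plan. It does not reconcile the text, because Section 4.3 names the same role that Section 6.2.3 calls blind.

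Several stronger readings are tempting, and the documents do not support them:

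- *The trial's blinding fails as a whole, for every participant.* Blinded data entry, blinded principal investigators and participants' blinding to the hypotheses are all stated, and the custody statements do not contradict them.
- *The statistician knows every arm.* The list gives envelope to arm, and no section says that the statistician holds the link to participants.
- *Blinding is the only protection for the analysis.* The model, the seven time points, the time-by-treatment term and the intention-to-treat set are all prespecified in Section 9.7.
- *The cortisol transformation is a further free choice.* Section 9.7 states a rule, a log transformation if values are non-normal. It gives no test for this, but the measure is an exploratory mediator.
- *Unblinded receipt lets staff choose which diaries to pursue.* No section gives the receiver that discretion. The follow-up callers are unblinded by design, whoever opens the mail. The primary outcome is self-reported, so receipt offers little scope to alter values.

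**Conclusion.** The contradiction over the statistician is in the current text. Sections 3, 4.3 and 9.3 cannot be followed as written with the blinding in Sections 6.2.3 and 10.1 assured. The conclusion is limited: the statistician's blinding is not secured. It does not say that it has been broken.

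The consequence falls mainly on covariate selection and missing-data handling in the primary analysis. The documents give no basis for sizing a bias. Resolving the conflict would change neither the sample size nor alpha nor power.

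This rests on the supplied text describing no separate unblinded statistician and no masking. A Delegation of Authority Log that assigns custody elsewhere would remove the practical risk, but the protocol wording would still need correcting.

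The conflict over data receipt is softer, because it depends on whether the Section 10.1 sentence is read as general or as confined to baseline materials.

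**What to change.** 1. Have a member of the existing statistical team who does no analysis generate and hold the randomisation list and the case assignment spreadsheets.
2. Give the study statistician data with masked arm codes only, until lock.
3. Withhold variables that reveal the arm until then: hypnotizability scores and practice-log comments. Without this step the masking fails.
4. Amend Sections 3, 4.3 and 9.3 to match Sections 6.2.3 and 10.1, and settle in the same edit whether the staff who randomise hold the list.
5. Replace the two statements on data receipt with one. For example, an unblinded staff member receives the mail and hands it over by study ID to a blinded data collector.

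The cost is protocol wording and a change of file access, with no new staff if an existing team member takes custody. If the study statistician already holds the list, rewording will not restore the blinding. The access should then be recorded, and the covariate set and the imputation rule fixed in writing before lock.

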6.2.3 Follow-up Visits

Week 1-6: Eligible participants will be randomly allocated to either a self-administered hypnosis group or a self-administered sham white noise hypnosis control group. Both groups will meet with a study research assistant two times (at baseline and at randomization/education visit) in person (or by telephone or video conference during COVID-19 restrictions) and further contact will be by phone through week 6 of the intervention period.

The interventions will be delivered through pre-recorded digital audio files, flash drives or CD's. For participants who prefer a flash drive or CDs, those will be provided. Additionally, if a participant prefers to use CDs, but does not have a CD player, one will be provided. Prepared self-management booklets will also be provided to each participant.

Participants in the self-administered hypnosis group and the self-administered sham white noise hypnosis group will use the self-management materials (booklets and audio recordings) for six weeks. A second kit to collect saliva and a Polar V800 HRV monitor will be mailed to participants during week five to be used for Week 6 data collection. At the end of Week 6, they will collect two days of saliva samples. HRV data will also be collected during the two days of saliva collection (as done during the baseline week) and both will be returned immediately following collection via a pre-posted mailer. However, if this collection was optional or unable to be completed due to COVID-19 restrictions, saliva samples and HRV data will not be collected at this time. At the end of Week 6, participants will return the completed hot-flash daily diaries, the self-hypnosis practice log, the questionnaire booklet with outcome measures of daily activity interference, quality of life, sleep disturbance, anxiety and stress in the provided pre-posted mailer. Due to COVID-19 restrictions, participants will also have the option of returning materials electronically (e.g., through DocuSign).

